6.1 Investigational product

Restylane Defyne is a sterile, biodegradable, transparent gel of non-animal cross-linked HA with the addition of lidocaine hydrochloride 3 mg/mL. The gel is supplied in a prefilled plastic syringe. The syringe contains 1 mL gel. The investigational product is for single use only.

6.2 Additional products and materials

The study site will provide pregnancy tests (urinary human chorionic gonadotropin; U-HCG) and needles as needed.

Local anaesthesia (topical or infiltration) may be used at the discretion of the treating Investigator before the treatment. If used, the anaesthesia shall be supplied by the study site. Type of anaesthesia, product name, and quantity used must be recorded in the eCRF.

The Investigator shall provide adequate equipment in case of emergency.

The sponsor will provide photo equipment as agreed when needed.

6.3 Packaging, labelling, and storage

6.3.1 Investigational product

Standard commercially available products will be used.

In addition to the standard labelling of the device, a study-specific label will be attached to the box containing study specific information in addition to applicable local labelling requirements.

The investigational products syringes shall be stored in their original packaging at a temperature up to 25°C protected from sunlight and freezing. Opened packages or partially used devices shall not be reused. The expiry date is indicated on package.

Detailed product information is provided in the IFUs, which is delivered with each study product.

6.4 Product accountability

The study products will be released to the PI or his/her authorized designee after study approvals have been received from the IEC, the CTA has been signed by all parties, site initiation visit has been performed and all essential documents are in place.

The PI must ensure that the study products are kept in a secure location, with access limited to those authorized by the PI.

The study products must be traceable from the manufacturer(s) to their use in subjects until return or disposal. It is therefore important that the PI maintains accurate product accountability records, i.e. documentation of the physical location of all study products, deliveries, and return of study products between the Sponsor and the PI, and documentation of administration of product to the subject. A shipping record shall be kept of all study products received from the Sponsor; including product name, date received, batch or lot

number, expiration date, and amount received. In addition, dispensing logs shall be maintained including the product name, batch number, expiry date, dispense date, the number of syringes used, the subject receiving investigational product, and number of syringes left in stock at the site.

When the study is completed, all unused or expired study product at each study site shall be returned to the Sponsor for destruction or be destroyed locally at the site, with proper documentation, after agreement with the Sponsor. Any malfunctioning study products shall be reported as described in section 8.2.3.

Products deliberately or accidentally destroyed during shipment or at a study site shall be accounted for and documented. Used syringes, disposable needle, and any opened unused material must be discarded immediately after the treatment session and must not be reused due to risk for contamination of the unused material and the associated risks including infections according to standard procedures at the site. Disposal of hazardous material, i.e. syringes and needles must conform to applicable laws and regulations.

All study product(s) sent to the PI will be accounted for and no unauthorized use is permitted.

6.5 Treatment

6.5.1 Treatment procedure

Before treatment the subject will be informed about the potential risks involved with the treatment and when to contact the Investigator in case of emerging symptoms.

The investigational product is reserved for use by doctors who have been trained in the appropriate injection techniques.

Injection procedures are associated with a risk of infection. Aseptic technique and standard practice to prevent cross-infections should be observed at all times including the use of disposable gloves during the injection procedure. All traces of make-up should be removed prior to any injection. The treatment site should be cleaned with a suitable antiseptic solution (extend at least five cm around the injection site).

Injection technique

The injection technique is important for the aesthetic effect of the treatment. The injection technique is at the discretion of the treating Investigator. The same predominant injection technique should be used for all subjects per site to limit variability due to technique.

6.5.2 Treatment regimen (dose and interval)

Down-up

Baseline - The chin and surrounding area to be treated with up to 2 mL of Restylane Defyne per treatment site with a maximum of 4 mL in total.

Week 3 – NLFs/MLs to be treated with up to 2 mL/line per NLF and up to 2 mL per ML of Restylane Defyne.

Week 6 - Optional touch-up in any of the treated areas that have not obtained optimal aesthetic improvement. Up to 2 mL per facial half is recommended for NLF and ML in combination, and a total of 2 mL in the chin and surrounding area.

Sufficient amount of study product should be injected to achieve optimal correction as agreed between the Treating Investigator and subject.

GALDERMA

Table 05DF1910 Clinical Study Protocol

MA-42248

Top-down

Baseline - NLF and ML to be treated with up to 2 mL per NLF and up to 2 mL per ML of Restylane Defyne.

Week 3 – The chin and surrounding area to be treated with up to 2 mL of Restylane Defyne per treatment site with a maximum of 4 mL in total.

Week 6 - Optional touch-up in any of the treated areas that have not obtained optimal aesthetic improvement. Up to 2 mL per facial half is recommended for NLF and ML in combination, and a total of 2 mL in the chin and surrounding area.

Sufficient amount of study product should be injected to achieve optimal correction as agreed between the Treating Investigator and subject.

A total of up to 12 mL of study product is to be injected at the treatment visits (visit 2 and 3) and up to 6 mL during the optional touch-up at visit 4.

6.5.3 Post-treatment care

The injected sites could be gently moulded by the treating Investigator to conform to the contour of the surrounding tissues. Topical cooling may be applied to reduce initial swelling and bruising. After the injection, some common injection-related reactions might occur. These reactions include erythema, swelling, pain, itching, bruising or tenderness at the implant site. Typically, resolution is spontaneous within one week after injection into the skin.

The subject must avoid exposing the treated area to heat (sun bathing, sauna, steam baths, etc.) or extreme cold until any signs of initial swelling and redness have disappeared.

6.5.4 Post-trial provisions

In time the implant will be degraded in the body and additional treatments will be necessary to maintain the aesthetic result. After the study is finalised Q-Med AB will not supply any more treatments to the subjects, but the investigational products are commercially available if the subjects would like to have additional treatments.

6.5.5 Electronic case report form recordings

The treatment is a gel injected by the Investigator and the following details of the injection are to be recorded in the eCRF:

- Local anaesthetic used (product name, amount applied, application date, and concentration)
- · Date for administration
- Administered volume
- Injection technique, see list below.
- Depth of injection
- Area of injection
- Post-treatment care (e.g. moulding, ice-pack)
- Use of needle
- Size of needle

In addition, any technical problems (device deficiencies) or clinical complications associated with the injection will be recorded in the eCRF.

Injection technique to be recorded in source data and the eCRF[‡]:

- Antegrade linear threading: also called push-ahead technique as some product is pushed ahead of the needle. Once the needle is in place, the product is injected ahead while inserting the needle in the tissue.
- Retrograde linear threading: the needle is threaded into the tissue at the appropriate depth, and the product in injected as a straight line on withdrawal of the needle
- Serial puncture: numerous small needle insertions to deliver a small amount of the product, repeated along a line or regions of the tissues
- Micro-bolus: small aliquots of the product is injected along a line or regions of the
- Fanning: a number of linear threads to spread the product over a wider area
- Cross-hatching: combines multiple injections of linear threading that crisscross at right angle to provide volume in a square shape
- Other: at the choice of the treating Investigator

6.5.6 Treatment compliance

Treatment compliance is fulfilled if the treating Investigator has injected sufficient amount of study product to achieve optimal correction. Any deviations to the treatment procedure shall be recorded in the deviation log and might be reason to categorize the treatment as not compliant.

7. Efficacy Assessments

7.1 General information

The methods for collecting efficacy data include 2D photography (section 7.2), GAIS (section 7.3), naturalness (7.4), subject satisfaction questionnaire (7.6), and a section 4.7).

At treatment visits, all assessments must be performed before study treatment is administered.

To avoid inter-observer variability, every effort should be made to ensure that the same individual who made the initial screening or baseline determinations completes all corresponding follow-up evaluations.

7.2 2D Photography

Photographs shall be taken prior to the injections of the investigational product when applicable and at follow-up visits in order to document treatment effect.

Note that no covering make-up shall be used on the photographs.

At visits where injections are performed, the photographs shall be taken prior to the injections and should include a front, 45°-front lateral, and profile picture.

Instructions for photography are provided in a separate photography manual. Each photograph shall be labelled with the subject number, and the visit number at which the photograph was taken. In order to maintain confidentiality, the photographs must not include any information that may reveal the subject's identity. The photographs should be used in the assessment of GAIS,

AEs. The photographs shall be presented on a computer monitor (preferably the same monitor throughout the study).

Photographs shall be taken at the time points indicated in the schedule of events (section 4.7).

Doc id 05DF1910 Clinical Study Protocol 👶 GALDERMA MA-42248

Global Aesthetic Improvement Scale (GAIS)

The GAIS is a qualitative 5-graded scale evaluating aesthetic improvement (Table 3). While GAIS is neither an objective measurement tool nor a validated tool, GAIS improvement has been commonly accepted by the medical community in Europe and the United States as clinical meaningful scale to assess visible aesthetic results. The GAIS can be used not only by the Investigator, but is also a useful tool for

Table 3. Global Aesthetic Improvement Scale (GAIS)

Rating (for the CCI)	Description (for the Investigator and CCI)
Very much improved	Optimal cosmetic result for the subject.
Much improved	Marked improvement in appearance from the original condition, but not completely optimal for this subject.
Improved	Obvious improvement in appearance from the original condition.
No change	The appearance is essentially the same as the original condition.
Worse	The appearance is worse than the original condition.

Source: Adapted from Narins et al. 200311.

and Investigator shall, independently of each other, rate the lower face for aesthetic change by comparing the appearance at follow-up against a photograph taken before treatment. The photographs shall be presented on a computer monitor (preferably the same monitor throughout the study). The Investigator will perform a live assessment . The following question will be asked: "How would you

describe the subject's aesthetic appearance of the lower face, i.e. the treated area, compared to the photographs taken before treatment?" The shall rate according to the left column in Table 3 and the Investigator shall rate according to the right column in Table 3, the scores for and Investigator rating are comparable.

A clinically significant improvement is defined as a score of improved; much improved; or very much improved. The GAIS assessments shall as far as possible be performed by the same Investigator throughout the study.

Naturalness,

[figure not shown]
will answer the questions regarding naturalness, Both the Investigator and according to Appendix 5 (Investigator's questionnaire) and Appendix 6 respectively.

Doc id 05DF1910 Clinical Study Protocol 🚣 GALDERMA MA-42248

Subject Satisfaction Questionnaire

The subjects will assess subject satisfaction, result at visit 2 – 5 (baseline, week 3, 6 and 9), before treatment with study product, when applicable (Appendix 9). Question 1, 2, 3 and 6 will be removed from the baseline questionnaire and question 2 from week 3.

Safety Assessments

8.1 Adverse events

8.1.1 Definition of an adverse event (Medical Devices Regulation (MDR) article 2(57))

An AE is any untoward medical occurrence, unintended disease or injury, or untoward clinical signs (including abnormal laboratory findings) in subjects, users or other persons[§], in the context of a clinical investigation, whether or not related to the investigational device.

This definition includes:

- a) events related to the investigational product or the reference product
- events related to the procedures involved
- events that are anticipated as well as unanticipated

8.1.2 Definition of a serious adverse event (MDR article 2(58))

A serious adverse event (SAE) is any AE that:

- a) led to death,
- b) led to serious deterioration in the health of the subject, that either resulted in
 - 1. a life-threatening** illness or injury, or

[§] For users or other persons, this definition is restricted to events related to the investigational product.

- 2. a permanent impairment of a body structure or body function, or
- hospitalization or prolonged hospitalization^{††}, or
- medical or surgical intervention to prevent life-threatening illness or injury or permanent impairment to a body structure or a body function,
- chronic disease
- led to fetal distress, fetal death, or a congenital physical or mental impairment or birth defect

In cases of doubt, whether an AE fulfils a serious criterion or not, there should be a predisposition to report as a SAE rather than not report as such (see section 8.1.4).

8.1.3 Recording instructions

Each subject should be questioned about AEs at each study visit following signing of informed consent. The question asked should be: "Since your last clinical visit; have you had any health problems?". Information on AEs can also be obtained from signs and symptoms detected during each examination or from a laboratory test, observations made by the study site personnel, subject diaries, or spontaneous reports from the subjects or their relatives.

When an AE is related to a device deficiency (refer to section 8.2), including technical device malfunction, the AE shall be recorded on the AE form/module in the eCRF and the technical complaint shall be reported separately on the clinical study complaint form eCRF.

Investigators, or other study site personnel, shall record all AEs in the eCRF, including:

- a) Event term (recorded in standard medical terminology and avoiding abbreviations)
- b) Affected area
- c) Start date (first day with symptoms)
- d) Stop date (last day with symptoms)
- e) Intensity (mild, moderate, or severe according to definition in section 8.1.3.1)
- Seriousness (serious or not serious, according to definition in section 8.1.3.2)
- g) Causal relationship to study product or study product injection procedure (yes or no)
- h) Action taken (none, medication treatment, non-pharmacological treatment, or other procedures/tests, subject withdrawn)
- Outcome of the AE (ongoing, recovered, recovered with sequelae, death, chronic/ stable, not recovered at the end of the study)

The AE form/module in the eCRF must be signed and dated by the Investigator.

^{**} The term "life-threatening" in the definition of "serious" refers to an event in which the patient was at risk of death at the time of the event; it does not refer to an event which hypothetically might have caused death if it were more severe. (Source: ICH-E2A clinical safety data management: definitions and standards for expedited reporting).

^{††} Planned hospitalization for a pre-existing condition, or a procedure required by the CSP, without serious deterioration in health, is not considered a SAE. (Source: ISO 14155:2011).

• 6.1.55511.	Title 05DF1910 Clinical Study Protocol	Doc id
♣ GALDERMA	•	MA-42248

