3.1.2 Safety objective and endpoints

Objective:

To evaluate AEs collected throughout the study

Endpoint

Incidence, intensity, duration and onset of AEs collected from injection of study product to patient withdrawal or end of study (visit 5).

Design of the Study

General outline

This is a 12-week, randomized, male-female and site stratified, evaluator-blinded, multicentre study to evaluate the effectiveness and safety of Restylane Defyne when using two different injection approaches, stepwise down-up vs. top-down, when treating the lower face.

Approximately 60 subjects requiring augmentation and correction therapy in the chin, NLFs and MLs fulfilling all eligibility criteria will be enrolled in the study. The subjects will be randomized to one of two treatment groups, the first treatment group will receive injections in the chin area at baseline and in the NLFs and MLs at the visit 3 (week 3), the second group will undergo the same treatment but in reverse order. The two groups are referred to as downup and top-down. Male-female stratification will be applied in the randomization and the aim is to randomize 10 male subjects to each group.

[figure not shown]
Doe id 05DF1910 Clinical Study Protocol 🚣 GALDERMA MA-42248

Six weeks after the second treatment, at visit 4, an optional touch-up will be administered to subjects that have not obtained optimal aesthetic improvement as agreed between subject and Investigator.

The subject will return to the clinic for a final follow-up visit (visit 5) 9 weeks after the first treatment.

All efficacy study assessments will be performed before treatment and safety will be followed by AE and device deficiency reporting throughout the study.

The Investigator will assess, Global Aesthetic Improvement Scale (GAIS), naturalness/ and safety. The subject assessments include, subject satisfaction questionnaire.

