8.1.4 Reporting of adverse events

Adverse event reporting on each subject shall start at baseline (visit 2) after the subject has been randomized. The reporting shall continue during each follow-up visit (including

•	05DF1910 Clinical Study Protocol	Doc id
GALDERMA	•	MA-42248

telephone contacts and extra visits between planned visits) until the last scheduled visit in the study.

All AEs, non-serious as well as serious, are to be reported as an AE in the eCRF.

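### The only scheduled, scripted AE question comes 13 to 29 days after each injection, when the expected mild local reactions are typically over, so their incidence, duration and worst intensity risk being under-recorded or imprecise

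*Combined protocol and SAP*

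**What the plan says.** The safety endpoint in 3.1.2 is "Incidence, intensity, duration and onset of AEs". Section 8.1.1 counts anticipated events as AEs, so ordinary injection-site reactions belong in the data. For every AE, 8.1.3 requires the first and last symptomatic day and an intensity grade. Section 10.4 then summarises time to onset and duration by preferred term for related AEs.

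On collection, 8.1.3 states: "Each subject should be questioned about AEs at each study visit following signing of informed consent". The scripted wording is "Since your last clinical visit; have you had any health problems". The same section says that AE information can also come from examination findings, laboratory tests, "observations made by the study site personnel, subject diaries, or spontaneous reports from the subjects or their relatives". Section 8.1.4 extends reporting to "telephone contacts and extra visits between planned visits". Section 6.5.5 says that "clinical complications associated with the injection will be recorded in the eCRF", and 6.5.1 says that subjects are told before treatment "when to contact the Investigator in case of emerging symptoms".

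On the expected course of local reactions, 2.4 says a few days. Section 6.5.3 says: "Typically, resolution is spontaneous within one week after injection into the skin". The IFU in Appendix 3 also gives one week.

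**The concern.** The endpoint needs events dated to the day and graded at their worst. The scheduled method is an open question about health in general, with no mention of the injection site, asked after the commonest reactions should have gone. A subject may not think of a bruise that faded two weeks earlier as a health problem. One who does mention it must reconstruct when it began, when it ended and how bad it was.

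An event nobody mentions leaves no record, and 10.5 plans no imputation. A subject whose only reaction goes unmentioned is counted in 10.4 among those with no AE. The likely direction of error is that the product looks better tolerated than it is. Section 2.3 intends the results as a basis for treatment guidelines, so the absolute rates matter even though the safety analysis is descriptive.

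**Working it through.** The plan gives no figure for AE capture, so there is nothing to reproduce. The check compares the gap between injection and the next scheduled question with the protocol's own resolution time.

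**Inputs.** Table 1 windows, counted from visit 2: visit 3 at 21 ± 3 days (18 to 24), visit 4 at 42 ± 3 days (39 to 45), visit 5 at 63 ± 5 days (58 to 68). Injections are given at visits 2 and 3, with an optional touch-up at visit 4. Resolution is taken as day 7, the longer of the protocol's two statements.

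**Formulas.** Shortest gap = earliest next visit − latest injection visit. Longest gap = latest next visit − earliest injection visit. Time since resolution = gap − 7.

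| Injection → next visit | Nominal gap | Shortest | Longest | Days since a day-7 resolution |
|---|---|---|---|---|
| Visit 2 → 3 | 21 | 18 − 0 = 18 | 24 − 0 = 24 | 11 to 17 |
| Visit 3 → 4 | 42 − 21 = 21 | 39 − 24 = 15 | 45 − 18 = 27 | 8 to 20 |
| Visit 4 → 5 | 63 − 42 = 21 | 58 − 45 = 13 | 68 − 39 = 29 | 6 to 22 |

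Even the shortest permitted gap, 13 days, lies beyond one week. The result does not depend on where a visit falls in its window. Section 4.1 counts the six weeks to visit 4 from the second treatment, whereas Table 1 counts them from visit 2. These passages must be reconciled, but the 4.1 reading would lengthen the gap after the second injection, so it does not weaken the point.

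**What the other routes cover.**
- Treatment-day recording (6.5.5) and AE collection at the injection visit can catch reactions that start at once. They cannot supply later onset, peak intensity after the subject leaves, or a stop date.
- Examination, staff observation and photographs at the next visit have the same three-week delay as the question.
- Spontaneous contact (6.5.1) depends on the subject deciding that a symptom is worth reporting.
- Diaries and telephone contacts would close the gap, but neither is scheduled or described in the readable Table 1, in the visit lists of 4.8, or in 8.1.3 and 8.1.4.

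**Illustration only.** The documents give neither a true incidence nor a capture share, so both are assumed here. Recorded incidence = true incidence × share captured. With 50% to 90% captured:
- true 30% is recorded as 15% to 27%
- true 50% is recorded as 25% to 45%, that is 15 to 27 subjects instead of 30 out of 60
- true 80% is recorded as 40% to 72%

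**The case against.** The strongest reply is that the question is one route among several. Same-day reactions can be seen and recorded, and the injection date is captured, which anchors immediate onset. Longer-lasting problems such as lumps, displacement or infection, and the delayed inflammation described in the IFU, may still be present at a visit or be reported spontaneously. All of this stands, and it confines the problem to mild reactions that come and go between visits. A reader might infer that all AE data rest on the one question, or that under-recording is certain. The documents support neither; they show a risk of unknown size.

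A reader might also infer that there is no diary. That cannot be concluded: 8.1.3 names diaries as a source, and the subject-assessment rows and some footnotes of Table 1 are redacted. What can be said is that the readable AE sections describe no diary procedure.

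A third tempting inference is that unblinded staff will probe differently by group or site. Nothing in the documents suggests this. The script is the same for everyone, both groups receive the same product in the same areas in reverse order, and randomization is stratified by site and gender.

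Finally, a checklist at the same visits is still recall at about three weeks. That is correct: it helps incidence more than dating. It also remains true that this is a descriptive, on-label, post-market study whose local reactions are already listed in the IFU, which limits the severity of the point without removing it.

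**Conclusion.** The concern holds in a limited form. The only scheduled, structured elicitation in the readable text is one open question, asked 13 to 29 days after each injection and 6 to 22 days after a typical reaction would have ended at the latest time the protocol gives. For mild reactions that resolve between visits, incidence is at risk of under-recording, and duration and worst intensity are at risk of imprecision. This bears on absolute AE rates and timing, not on the contrast between down-up and top-down.

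The timing rests on the Table 1 windows and on the protocol's one-week resolution time. The amount of under-recording cannot be derived from the documents, and the illustrative percentages are assumptions. The diary element is conditional on what the redacted rows contain. This is a worthwhile, inexpensive improvement to a stated endpoint; it does not invalidate the study.

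**What to change.** - In 8.1.3, keep the open question and ask it first. Then, at visits 3, 4 and 5, ask about each of the six reactions named in 2.4 (bruising, swelling, erythema, tenderness, itching, pain), separately for the chin and for the NLFs/MLs, recording start date, stop date and worst intensity.
- In 10.4, tabulate these solicited reactions separately from volunteered AEs, and state which injection is the reference for days to onset.
- Because the checklist still relies on recall at about three weeks, describe onset and duration of resolved reactions as recalled. If the diary named in 8.1.3 is in use, schedule it for the days after each injection and refer to it in the AE section. If it is not in use, remove the mention.

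The cost is a short checklist at existing visits, one eCRF page and one extra table, with no added visits or change to treatment. The downside is that more mild events will be recorded, and solicited rates are not comparable with spontaneous ones, which is why they need their own table.
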